# 7.6 Handling of Biological Samples

A trial-specific laboratory manual will be provided to the participating sites, describing in detail how to handle, store, and transport the biological samples (blood) in this trial. The biological samples analysed at central laboratories will be maintained in storage after the end of the trial. Destruction will take place within 2 years after reporting of the trial. Exceptions are the blood samples collected for potential future analysis of possible biomarkers associated with ovarian response, as well as blood samples for which methods / results have not been adequately validated; these will be stored for a maximum of 10 years after reporting of the trial, prior to destruction in line with local regulations. Potential additional blood samples analysed at local laboratories as part of screening assessments or monitoring of the subject during the trial (e.g. criterion for triggering of final follicular maturation and evaluation of OHSS), will be destroyed after analysis. The processes related to handling of biological samples will be described in the Informed Consent Form, and biobank / data protection legislation including local legislation will be adhered to.

<sup>h ICMART and WHO glossary on ART terminology: Clinical pregnancy a pregnancy diagnosed by ultrasonographic visualization of one or more gestational sacs or definitive clinical signs of pregnancy. In addition to intrauterine pregnancy, it includes ectopic pregnancy.

# 7.7 Implications of COVID-19 Pandemic

The following considerations must be taken into account due to the current coronavirus disease 2019 (COVID-19) pandemic:

• Vaccination against COVID-19

Vaccination against COVID-19 will be recorded at screening as part of the subject's medical history and/or throughout the trial as concomitant medication, and should be reported using the term "COVID-19 immunisation". Based on the currently available information and the ESHRE position on COVID-19 vaccination and assisted reproduction, Ferring's risk assessment is that there will be no protocol-specific requirements on COVID-19 vaccination.

- Medical history related to COVID-19
   Past or ongoing occurrence of COVID-19 will be recorded at screening as part of the subject's medical history, and should be reported using the term "COVID-19".
- Adverse events related to COVID-19 In case of confirmed COVID-19 by a SARS-CoV-2 positive test, the term "COVID-19" should be used to report the adverse event irrespective of the type of test. In case of suspected COVID-19 infection, the term "Suspected COVID-19" should be used to report the adverse event. In case of recording concomitant medication against COVID-19, the indication should be "COVID-19" irrespective of the treatment.
- Missing visits / missing data

In case subjects are prevented from attending scheduled visits due to the COVID-19 pandemic, the investigator (or designee) will attempt to contact the subject by phone or other ways to inquire about potential adverse events and changes to concomitant medication. In case not attending scheduled visits due to the COVID-19 pandemic may have any implications in the drug accountability of IMP or NIMP, it should be documented by the trial medication delegate.

• Protocol deviations due to COVID-19 illness and/or COVID-19 control measures Protocol deviations should be avoided whenever possible except when necessary to eliminate an immediate hazard to the subject. If deviations occur they will be documented as per standard practice, with additional specification whether they were related to the COVID-19 pandemic.

### 8 ADVERSE EVENTS

#### 8.1 Adverse Event Definition

An adverse event is any untoward medical occurrence in a subject participating in a clinical trial. It includes:

- Any unfavourable and unintended sign, symptom or disease temporally associated with the use of the IMP, whether or not considered to be caused by the IMP.
- Adverse events commonly observed and adverse events anticipated based on the pharmacological effect of the IMP.
- Any laboratory abnormality, vital sign or finding from physical or gynaecological examination assessed as clinically significant by the investigator [note: pre-existing conditions diagnosed through assessments and examinations at the screening visit or during the screening period are not adverse events, but are recorded as medical history.]
- Accidental injuries, reasons for any change in medication (drug and/or dose), reasons for any medical, nursing or pharmacy consultation, or reasons for admission to hospital or surgical procedures.

All adverse events will be coded using MedDRA (the MedDRA version will be documented).

#### 8.2 Collection and Recording of Adverse Events

#### 8.2.1 Collection of Adverse Events

The investigator must monitor the condition of the subject throughout the trial from the time of obtaining informed consent until the last visit (end-of-trial visit). In addition, for subjects who undergo transfer in the fresh cycle, assessment of late OHSS (onset >9 days after triggering) will take place during the follow-up period.

The sources of adverse events cover:

- The subject's response to questions about his/her health (a standard non-leading question such as "How have you been feeling since your last visit?" is asked at each visit).
- Symptoms spontaneously reported by the subject.
- Investigations and examinations where the findings are assessed by the investigator to be clinically significant changes or abnormalities.
- Other information relating to the subject's health becoming known to the investigator (e.g. hospitalisation).

# 8.2.2 Recording of Adverse Events

The investigator must record all adverse events in the Adverse Event Log provided for each subject in the EDC with information about:

- Adverse event description
- Date and time of onset (time can be omitted, if applicable) [note: if date of onset of an event is the same as the date of informed consent or date of IMP administration, time is important and should not be omitted]
- Intensity
- Causal relationship to IMP
- Action taken to IMP
- Other action taken
- End date and time (time can be omitted, if applicable)
- Outcome
- Seriousness

Each of the items in the Adverse Event Log is described in detail in the following sections.

### Adverse Event

Adverse events should be recorded as diagnoses, if available. If not, separate signs and symptoms should be recorded. One diagnosis / symptom should be entered per record.

If a subject suffers from the same adverse event more than once and the subject recovers in between the events, the adverse events should be recorded separately. If an adverse event changes in intensity, a worst-case approach should be used when recording the event, i.e. the highest intensity and the longest duration of the event.i If a subject suffers from a pre-existing medical condition that worsens in intensity after signed informed consent, it should be recorded as an adverse event.

*Note*: a procedure is not an adverse event; the reason for conducting the procedure is. Hospitalisation is not an adverse event; the reason for hospitalisation is. Death is not an adverse event, but the cause of death is (an exception is sudden death of unknown cause, which is an adverse event).

<sup>i Exception: if an adverse event with onset before the first IMP administration (i.e. a pre-treatment adverse event) worsens in intensity after IMP administration, this must be recorded as two separate events. The initial adverse event should be recorded with outcome "not recovered", without recording end date and time. The second adverse event should be recorded with date and time of onset when the intensity changed.

# Date and Time of Onset

The date of onset is the date when the first sign(s) or symptom(s) were first noted. If the adverse event is an abnormal clinically significant laboratory test or outcome of an examination, the onset date is the date the sample was taken or the examination was performed.

### Intensity

The intensity of an adverse event must be classified using the following 3-point scale:

Mild:	Awareness of signs or symptoms, but no disruption of usual activities.
Moderate:	Disruption of usual activities (disturbing).
Severe:	Inability to work or perform usual activities (unacceptable).

# Causal Relationship to IMP

The possibility of whether the IMP caused the adverse event must be classified as one of the following:

Reasonable possibility:	There is evidence or argument to suggest a causal relationship
	between the IMP and the adverse event. The adverse event may occur
	as part of the pharmacological action of the IMP or may be
	unpredictable in its occurrence.

Examples:

- Adverse events that are uncommon but are known to be strongly associated with IMP exposure.
- Adverse events that are not commonly associated with IMP exposure, but the event occurs in association with other factors strongly suggesting causation, such as a strong temporal association or the event recurs on rechallenge.
- No reasonable possibility: There is no reasonable evidence or argument to suggest a causal relationship between the IMP and the adverse event.

Examples:

- Known consequences of the underlying disease or condition under investigation.
- Adverse events common in the trial population, which are also anticipated to occur with some frequency during the course of the trial, regardless of IMP exposure.

An adverse drug reaction is defined as an adverse event assessed to be related to the administration of IMP with a reasonable possibility.

#### Action Taken to IMP

The action taken to the IMP in response to an adverse event must be classified as one of the following:

- No change (medication schedule maintained or no action taken)
- Discontinued
- Interrupted
- Dose reduced
- Dose increased

### **Other Action Taken**

Adverse events requiring therapy must be treated with recognised standards of medical care to protect the health and well-being of the subject. Appropriate resuscitation equipment and medicines must be available to ensure the best possible treatment of an emergency situation.

If medication is administered to treat the adverse event, this medication should be entered in the Concomitant Medication Log.

#### Date and Time of Outcome

The date and time the subject recovered or died.

#### Outcome

The outcome of an adverse event must be classified as one of the following:

- Recovered (fully recovered or the condition has returned to the level observed at initiation of trial treatment)
- Recovered with sequelae (resulted in persistent or significant disability / incapacity)
- Recovering (the event is improving)
- Not recovered
- Fatal

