### NUMBER OF SUBJECTS

The total number of subjects to be randomised is approximately 300, i.e. 200 randomised to treatment with REKOVELLE and 100 randomised to treatment with GONAL-F.

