### Withdrawal of Consent

If the subject withdraws her consent, no further data will be obtained. However, already obtained samples may be analysed. This will be described in the Informed Consent Form. The subject can request destruction of samples which would otherwise have been kept in storage.

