#### 8.5 Serious Adverse Events

#### 8.5.1 Serious Adverse Event Definition

#### Serious Adverse Events during the Trial

An event is defined a serious adverse event if it:	Guidance
results in death	Any event resulting in a fatal outcome must be fully documented and reported, including deaths occurring within four weeks after the treatment ends and irrespective of the causal relationship to the IMP. The death of a subject enrolled in a trial is per se not an event, but an outcome.
is life-threatening	The term life threatening refers to an adverse event in which the subject was at immediate risk of death at the time of the event. It does not refer to an event, which may have caused death if it were more severe.
requires in-patient hospitalisation or prolongation of existing hospitalisation	The term hospitalisation means that the subject was admitted to hospital or that existing hospitalisation was extended as a result of an event. Hospitalisation describes a period of at least 24 hours. Over-night stay for observation, stay at emergency room or treatment on an out-patient basis do not constitute a hospitalisation. However, medical judgement must always be exercised and when in doubt the case should be considered serious (i.e. if case fulfils the criterion for a medically important event). Hospitalisations for administrative or social purposes do not constitute a serious adverse event. Hospital admissions and/or surgical operations planned before trial inclusion are not considered adverse events, if the illness or disease existed before the subject was enrolled in the trial, provided that the condition did not deteriorate during the trial.
results in persistent or significant disability / incapacity	Disability / incapacity means a substantial disruption of a person's ability to conduct normal life functions. In doubt, the decision should be left to medical judgement by the investigator.
is a congenital anomaly / birth defect	Congenital anomaly / birth defect observed in any offspring of the subject conceived during treatment with the IMP.

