# 9.9 Adverse Events

Adverse events will be grouped according to start of IMP as follows:

- Pre-treatment adverse event, i.e. any adverse event occurring after signed informed consent and before the first dose of IMP, or a pre-existing medical condition that worsens in intensity after signed informed consent but before the first dose of IMP.
- Treatment-emergent adverse event, i.e. any adverse event occurring after the first dose of IMP and before the end-of-trial visit, or a pre-treatment adverse event or pre-existing medical condition that worsens in intensity after the first dose of IMP and before the end-of-trial visit.

<sup>k Note this includes OHSS with onset during stimulation or before triggering.

Treatment-emergent adverse events will be presented in summary tables and listings. Pre-treatment adverse events will be presented in a listing only. Treatment-emergent adverse events will be summarised overall and tabulated by System Organ Class (SOC) and Preferred Term (PT). The total number of subjects reporting an adverse event, the percentage of subjects with an adverse event, and the number of events reported will be described.

Summary tables will be produced for the following: all adverse events, adverse events by causality (reasonable possibility / no reasonable possibility), adverse events leading to death, adverse events by intensity (mild / moderate / severe), adverse reactions by intensity (mild / moderate / severe), serious adverse events, adverse events leading to discontinuation, adverse events with an incidence of  $\geq$ 5% in any treatment group, and non-serious adverse events with an incidence of  $\geq$ 5% in any treatment group.

For adverse events, a worst-case approach will be used for causality, intensity, seriousness, and outcome, in case these would be missing. If the timing of the onset of an adverse event cannot be established in relation to IMP, it will be considered as a treatment-emergent adverse event.

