## 11.2 Adverse Events

Adverse events will be grouped according to start of IMP as follows:

• Pre-treatment adverse event, i.e. any adverse event occurring after signed informed consent and before the first dose of IMP, or a pre-existing medical condition that worsens in intensity after signed informed consent but before the first dose of IMP.

• Treatment-emergent adverse event, i.e. any adverse event occurring after the first dose of IMP and before the end-of-trial visit, or a pre-treatment adverse event or pre-existing medical condition that worsens in intensity after the first dose of IMP and before the end-of-trial visit.

Treatment-emergent adverse events will be presented in summary tables and listings. Pre-treatment adverse events will be presented in a listing only. Treatment-emergent adverse events will be summarised overall and tabulated by System Organ Class (SOC) and Preferred Term (PT). The total number of subjects reporting an adverse event, the percentage of subjects with an adverse event, and the number of events reported will be described.

Summary tables will be produced for the following treatment-emergent adverse events: all adverse events, adverse events by causality (reasonable possibility / no reasonable possibility), adverse events leading to death, adverse events by intensity (mild / moderate / severe), adverse reactions by intensity (mild / moderate / severe), serious adverse events, adverse events leading to discontinuation, adverse events with an incidence of  $\geq 5\%$  in any treatment group, and non-serious adverse events with an incidence of  $\geq 5\%$  in any treatment group.

For adverse events, a worst-case approach will be used for causality, intensity, seriousness, and outcome, in case these would be missing. If the timing of the onset of an adverse event cannot be established in relation to IMP, it will be considered as a treatment-emergent adverse event.

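### The worst-case rule for missing adverse event outcomes does not exclude Fatal, so read literally a blank outcome field could be counted as a death

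*Combined protocol and SAP*

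**What the plan says.** The rule appears in both documents. Protocol 9.9 reads: "For adverse events, a worst-case approach will be used for causality, intensity, seriousness, and outcome, in case these would be missing". SAP 11.2 repeats it, and SAP section 13, which lists the changes from the protocol, leaves it alone.

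The scale to which the rule applies is in protocol 8.2.2, under Outcome: "The outcome of an adverse event must be classified as one of the following". Five categories follow: Recovered, Recovered with sequelae, Recovering, "Not recovered" and Fatal. There is no category for an unknown outcome.

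Protocol 9.9 and SAP 11.2 also list the summary tables for treatment-emergent events. One of them covers adverse events leading to death. None is broken down by outcome.

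Protocol 4.3.3 describes one way in which follow-up of an event can end early: "If the subject withdraws her consent, no further data will be obtained". Real deaths have a separate reporting duty in protocol 8.5.1: "Any event resulting in a fatal outcome must be fully documented and reported".

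**The concern.** For causality, intensity and seriousness a worst-case rule is ordinary conservatism: a doubtful event is counted as related, severe or serious. Outcome is different, because the extreme of its scale is not a degree of caution but a specific fact, the death of the subject. A missing entry is no evidence of that fact.

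Comparison of the safety profiles is a stated secondary objective, and subjects must be in good physical and mental health to enter. My assumption, which the documents do not quantify, is that few if any deaths would be expected over one stimulation cycle. Even a single imputed one would then stand out in the report. It would also be at odds with the rest of the record, since protocol 8.5.1 makes any event that results in death a serious adverse event, with full documentation.

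**Working it through.** The plan gives no figure on this point, so there is none to reproduce. The check is a reading of the rule against the scale, followed by simple percentages.

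**Step 1: what the rule yields.** The rule (protocol 9.9, SAP 11.2) replaces a missing outcome by the worst case. The admissible values (protocol 8.2.2) are the five listed above, and the worst is Fatal. I looked for text that would stop the rule at Not recovered, rank the categories, or require a recorded death, and found none in protocol sections 8 and 9 or in SAP sections 11 and 13.

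**Step 2: how the SAP uses the term elsewhere.** SAP section 10 replaces missing counts of oocytes, fertilised oocytes and blastocysts by zero whatever the reason, and calls this worst-case imputation. There the term means the extreme value of the scale. A programmer who carried that usage into section 11.2 would arrive at Fatal.

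**Step 3: where an imputed value could land.** Of the listed summary tables, the one on events leading to death is the natural user of a fatal outcome. Pre-treatment events go to a listing only, so the exposure is confined to treatment-emergent events. Neither document says whether the deaths table is derived from the outcome field after imputation; step 4 assumes that it is.

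**Step 4: size per case.** The planned allocation is "200 randomised to treatment with REKOVELLE and 100 randomised to treatment with GONAL-F". The tables report percentages of subjects, so the unit is a subject with at least one blank outcome. The safety set contains exposed subjects only, so the denominators could be slightly smaller than these.

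| Subjects with an imputed Fatal | If in REKOVELLE (n = 200) | If in GONAL-F (n = 100) |
|---|---|---|
| 1 | 1/200 = 0.5% | 1/100 = 1.0% |
| 2 | 2/200 = 1.0% | 2/100 = 2.0% |

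**Step 5: direction.** Let p be the probability that a subject has a blank outcome, equal in both arms. The expected numbers are 200p and 100p. The expected percentages are 200p/200 = p and 100p/100 = p. The 2:1 allocation changes the counts but not the expected rates.

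**Step 6: frequency.** The documents state neither the number of events per subject nor the proportion with no outcome, so the expected number of affected subjects cannot be derived and may be zero.

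**The case against.** The strongest reply is that the rule will hardly ever be used, and that its extreme reading is an inference. Much of this stands.

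- No text names Fatal as the imputed value. A reader might infer that the plan reports every event without an outcome as a death. The documents do not say so; they only fail to exclude it.
- A reader might also infer that an event still open when a subject withdraws consent becomes fatal. That does not follow. An open event can be coded Recovering or Not recovered from what is known at that moment. A footnote in protocol 8.2.2 shows the convention: a pre-treatment event that later worsens is recorded as not recovered, with no end date. Withdrawal stops new data; it does not blank the last known status.
- Outcome is a required log item, events are followed to the last visit (protocol 8.6.1), and the investigator signs the data entries (protocol 10.2). Truly blank outcomes should therefore be rare.
- A real death has its own route, with notification within 24 hours (protocol 8.5.2). An imputed Fatal would have no matching serious adverse event report, so the mismatch would be visible.

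What remains is narrow. The rule exists only for outcomes that are still missing after all these safeguards, and in exactly those cases its literal result is wrong. Visibility is a partial remedy: someone would have to override a pre-specified rule, possibly after the blind is broken, and the SAP should not leave that to judgement.

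**Conclusion.** The rule is wrong as written for outcome, with small practical impact. Taken literally, it permits a treatment-emergent event with a blank outcome to be counted as fatal and to enter the deaths table, at 0.5% of the REKOVELLE arm or 1.0% of the GONAL-F arm per affected subject. This rests on two assumptions: that worst case means the extreme category, as in SAP section 10, and that the deaths table draws on the imputed field.

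Two stronger conclusions are not supported. The first is that imputed deaths would bias the comparison against REKOVELLE because its arm is larger: with equal missingness the expected percentages are equal, and a single case weighs more in the smaller GONAL-F arm. The second is that a definite number of false deaths should be expected, or that the safety conclusion would change: the documents give no missingness rate, and safety is tabulated without a formal test. The efficacy analyses and the sample size are not affected.

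**What to change.** In SAP 11.2, either remove outcome from the worst-case rule, or state that a missing outcome is reported as missing or unknown, or as Not recovered. Add that Fatal, and the table of adverse events leading to death, rest only on documented deaths. Keep the worst-case rule for causality, intensity and seriousness.

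SAP section 1 says that the SAP reflects the updated analyses where it differs from the protocol, so the SAP sentence is enough, with a line in section 13 to record the change. An extra unknown category in the protocol's outcome list is not needed, and it could make incomplete recording easier. The cost is one or two sentences before database lock, with no new data, no additional subjects and no loss of conservatism for the other three attributes.
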